Forty two patients were randomly assigned to either the Group 1 (n=22, sedation and analgesia without any airway instrumentation) or Group 2 (n=20, airway control provided by GLT after inducing sedation and analgesia). Also, randomization (1:1) was based on a computer generated random numbers table, using MedCalc v. 16 statistical software for Windows (medcalc.com.tr). All patients received standard intervention procedures determined by the same team of cardiologists and an anesthesiologist with experience in TEE. Standard intervention procedure protocol was not change in any way.

All patients received preoperative midazolam (0.01-0.02 mg/kg) before being taken to the procedure room. For patients in Group 1, a standardized sedation and analgesia was administered by an experienced anesthesiologist. After administration of lidocaine (1 mg/kg) and atropine sulfate (0.01 mg/ kg), and also preoxygenation (100% 4 L/min O2 for 3 min), patients were induced with propofol (1-2 mg/kg) and fentanyl (1-2 mcg/kg) via intravenous (IV) route at doses calculated according to ideal body weight. Anesthesia was maintained with propofol infusion (4 mg/kg/h). Repetitive IV boluses of propofol (0.1 mg/kg) were administered, if necessary. Patients received oxygen (100%, 3 L/min) through a nasal cannula during sedation and analgesia.

For patients in Group 2, after administration of lidocaine (1 mg/kg) and atropine sulfate (0.01 mg/ kg), and also preoxygenation (100% 4 L/min O2 for 3 min), patients were induced with propofol (1-2 mg/kg) and fentanyl (1-2 mcg/kg). After induction of anesthesia, supraglottic airway device named GLT (VBM Medizintechnik GmbH, Sulz, Germany) was inserted (Figure 3). Patients were ventilated mechanically with a tidal volume of 6–8 mL/kg

based on ideal body weight and a frequency of 12–14 breaths/min using a Dräger Primus ventilator (Dräger AG, Lübeck, Germany) after inserting the GLT. Repetitive IV boluses of propofol (0.1 mg/kg) were administered, if necessary. Also, GLT was then removed at the end of TEE procedure.

The anesthesiologist was responsible for patient comfort, hemodynamic stability, immobility, adequate analgesia and airway management.

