We hypothesized that GLT, allowing passage of the TEE probe and ensuring supraglottic airway control, would provide more advantages in terms of hemodynamic stabilization, complications related airway management, cardiologist and patient satisfactions when used in a clinical setting. To date, there has been no detailed prospective clinical study analyzing the performance of the GLT during TEE. The present study sought to address this gap by performing a prospective clinical study to analyze the performance of the GLT during TEE. Our primary outcome measures were safety of airway management, and cardiologist and patient satisfactions. Our study also recorded demographic characteristics, intraoperative and postoperative hemodynamics, level of hypoxemia, and duration of procedure as secondary outcome measures.

Statistical Analysis

Data were analyzed using the Statistical Package for the Social Sciences program (SPSS 22.0; IBM). The Shapiro Wilk normality test was used to test whether quantitative variables showed a normal distribution. Differences between variables in two groups with normal distribution were compared with the paired t-test. Continuous variables distributed abnormally were compared between the groups using a Mann–Whitney U test. Differences between variables within the same group at different times were tested with the Friedman test, and significant variables had pairwise comparisons performed with the Dunn test. Categorical variables were summarized using frequencies and percentages, and were compared between the groups using a chi-square test or Fisher's exact test. Descriptive statistics are given as mean, standard deviation, median, Q1 (1st quartile), Q3 (3rd quartile), frequency and percentage (%). Results were evaluated at a 95% confidence interval at a significance level of p < 0.05. Consent to conduct the study was obtained from Local Ethic Committee of Bezmialem Vakif University.

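### The plan names no between-group test for ordered categories, so any satisfaction or hypoxemia outcome recorded in three or more grades would be tested with its ordering discarded

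*Combined protocol and SAP*

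**What the plan says.** The Statistical Analysis section offers two kinds of between-group comparison.

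- **Quantitative variables** are checked for normality and go to a t-test if normal. Otherwise: "Continuous variables distributed abnormally were compared between the groups using a Mann–Whitney U test".
- **Categorical variables**: "Categorical variables were summarized using frequencies and percentages, and were compared between the groups using a chi-square test or Fisher" exact test.

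The Friedman and Dunn tests are for changes over time within a group and do not compare the arms. No trend test, proportional-odds model or rank test is named for ordered categories.

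The outcomes are listed at the end of the Study Protocol section. The primary ones: "Our primary outcome measures were safety of airway management, and cardiologist and patient satisfactions". The secondary list includes "level of hypoxemia, and duration of procedure as secondary outcome measures". No scale, grade definition, cut-off or number of levels is given for any of them. Peripheral oxygen saturation appears under standard monitoring and is a numeric measure.

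The arms are small, 22 and 20, and the documents contain no sample-size or power calculation.

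**The concern.** Satisfaction is a judgement of more or less. If it is recorded in more than two categories, those categories have an order. An unordered chi-square or Fisher test gives the same p-value whichever way the grade labels are shuffled. With k grades it spreads its power over k - 1 degrees of freedom, while the hypothesis of greater satisfaction with the gastro-laryngeal tube concerns one direction along the scale.

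At stake is the chance of detecting a real difference, in either direction, on two of the three primary outcomes in a trial of 42 patients. Because the scales are not stated, the plan also leaves open whether a rating counts as categorical (chi-square) or quantitative (Mann-Whitney). Those two routes can lead to different conclusions from the same data.

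**Working it through.** The documents give no power or effect-size figure, so there is no stated figure to reproduce. The check asks how much power the unordered test loses if an outcome is graded.

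**Inputs from the documents**

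- Arms: 22 v 20 (Study Protocol: "Forty two patients were randomly assigned to either the Group 1 (n=22, sedation and analgesia without any airway instrumentation"; Group 2 has 20).
- Significance level 0.05 (Statistical Analysis); two-sided is assumed, as the sidedness is not stated.

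**Assumptions, because the documents are silent**

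- 2 to 5 ordered grades, with several control-arm distributions (even, skewed, peaked, rare upper grades).
- A proportional-odds shift: with control cumulative probability C_j, the other arm has cumulative odds [C_j / (1 - C_j)] / OR. Odds ratios run from 2 to 8.
- No dropout.

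**Example of the shift.** Four even grades have cumulative probabilities 0.25, 0.50, 0.75, so odds 1/3, 1, 3. Dividing by OR = 4 gives 1/12, 1/4, 3/4, hence cumulative probabilities 0.077, 0.200, 0.429 and grade probabilities 0.077, 0.123, 0.229, 0.571. The probability that a patient in the better arm scores higher, counting ties as half, is then 0.25 × (0.962 + 0.862 + 0.686 + 0.286) = 0.70.

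**Simulation.** Pearson chi-square on k - 1 degrees of freedom was compared with the tie-corrected Mann-Whitney test without continuity correction, 20,000 trials per case. At odds ratio 4 with an even control distribution:

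| Grades | Chi-square | Mann-Whitney | Loss (points) |
|---|---|---|---|
| 3 | 54% | 63% | 9 |
| 4 | 48% | 66% | 18 |
| 5 | 43% | 68% | 25 |

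Loss in points across the control distributions:

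| Grades | OR 2 | OR 3 to 6 | OR 8 |
|---|---|---|---|
| 2 | 0 | 0 | 0 |
| 3 | 4-5 | 8-10 | 4-7 |
| 4 | 7-8 | 14-19 | 9-11 |
| 5 | 10-12 | 21-27 | 15-20 |

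With two grades the tests coincide (37.7% each at OR 3, 73.1% each at OR 6).

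**Fisher's exact test** does not recover the loss. At odds ratios 3 to 6 its extension to more than two categories loses about 8-14 points with three grades, 12-18 with four and 17-30 with five. These rest on 1,500 trials per case (500 for five grades), so the last range has wide Monte Carlo error.

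**Analytic cross-check.** Give both tests the same noncentrality λ = (1.96 + z_power)², where z_power is the normal quantile of the rank test's power. At 70% power, λ = (1.96 + 0.524)² = 6.17. The chance that a noncentral chi-square with this λ exceeds its 5% critical value is:

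- 2 df (5.99): 59.7%, a loss of 10.3 points
- 3 df (7.81): 53.1%, a loss of 16.9 points
- 4 df (9.49): 48.2%, a loss of 21.8 points

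For rank-test power of 50% to 80% the losses are 9-11, 15-17 and 19-22 points, in line with the simulation.

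**Type I error** (OR 1): about 3-5% for chi-square and 4-5% for Mann-Whitney. Neither is inflated.

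**When the effect is not a shift.** With 0.3/0.4/0.3 in one arm and 0.1/0.8/0.1 in the other, chi-square has 68% power and Mann-Whitney 6%.

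**The case against.** The strongest objection is that no document says any of these outcomes is graded. Satisfaction could be yes/no, where nothing is lost, or a numeric score, where the plan already reaches Mann-Whitney. This stands, and it makes the point conditional.

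A reader might infer from the word level that hypoxemia is graded and will be compared by chi-square. The documents do not support that. Level is also an ordinary word for a numeric value, oxygen saturation is monitored as a number, and a saturation analysis would follow the quantitative rule. Nor does the hypothesis name hypoxemia: it names hemodynamic stability, airway complications and satisfaction.

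A reader might also attach a single figure, such as 15 to 25 points, to the loss. That fits only four or five grades with a moderate to large shift. Three grades, a small effect or a binary outcome give less.

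It is also fair to say that a significant chi-square result would not leave the direction unknown, because the plan reports frequencies and percentages. The test itself still does not address direction.

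Finally, the rank test does much worse when the arms differ in spread and not in level. That is true, but a hypothesis of greater satisfaction concerns level. None of this supplies the missing rule for ordered grades.

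**Conclusion.** The point holds in conditional form. The text contains no between-group test for ordered categories, and the scales that would show whether one is needed are not given. If cardiologist satisfaction, patient satisfaction or hypoxemia is recorded in three or more ordered grades, the stated rule discards the ordering. The cost is about 8-10 points of power with three grades, 14-19 with four and 21-27 with five.

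Those figures rest on 22 v 20 patients, two-sided 5%, a proportional-odds shift and odds ratios 3 to 6. At odds ratio 2 the cost is about 4-12 points. It is nil for a binary outcome or one analysed as a number.

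A reader might go further and conclude that the planned comparisons are invalid. The calculations do not support this, because type I error is not inflated. The issue is efficiency and a closer match between test and question. It deserves correction because it may touch two primary outcomes in a small trial and the remedy is already in the plan.

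**What to change.** State the scale of cardiologist satisfaction, patient satisfaction and hypoxemia: the number of levels, their definitions, and whether each is analysed as grades or as a number. Then add to the Statistical Analysis section:

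> Any outcome recorded in three or more ordered grades is compared between groups with the tie-corrected Mann-Whitney test and reported with a directional effect estimate (probability of a better score). Chi-square or Fisher is used only for binary or unordered variables. Hypoxemia analysed as numeric SpO2 follows the rule for quantitative variables.

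The cost is wording only: no new data, patients or methods, since Mann-Whitney is already named. If the outcomes prove binary or numeric, the addition changes nothing. The one downside is little power for a difference that is not a shift, such as more patients at both extremes in one arm, which the stated hypothesis does not concern. Tabulating the full grade distribution by arm, as the plan's frequencies and percentages already allow, would let a reader see such a pattern.
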